10.1.6 Primary Analysis with new missing data allocation windows

The primary analysis will be repeated but considering now the windows below to reallocate missing data:

- Visit 2: 7 to 21 days
- Visit 3: 35 to 49 days

10.2 Secondary Efficacy Analysis

All secondary endpoints evaluated through a mean absolute change will follow a similar statistical analysis as for the primary variable (ANCOVA, considering baseline corresponding endpoint evaluation as covariate and treatment and region as fixed factors):

- Mean changes of ESS (up to 2-week treatment period)
- Mean relative change in the Epworth Sleepiness Scale (ESS) from baseline to the end of the 2-week and 6-week treatment periods (percentage of absolute decrease compared to baseline ESS).
- SCOPA-Sleep (up to 2-week and 6-week treatment period)
- PDSS-2 (2-week and 6-week)
- MWT (6-week)
- Polysomnography (6-week)
 - o Sleep Efficiency
 - o Percentage of TST REM
- UPDRS Part III (2-week and 6-week)
- Motor function assessed by the wrist worn device (6-week)
- HAM-D (2-week, 6-week and follow-up)
- MoCA (6-week), and FSS (6-week).
- Fatigue Severity scale (FSS)
- Polysomnography (6-week): Baseline index will not be considered in these Logistic models.
 - o Events Index (Increase in Events Index)
 - o Arousal Index (Increase in Arousal Index)

Categorical variables as detailed below will be analysed through fitted logistic regression model adjusted on baseline corresponding endpoint evaluation as a covariate and treatment and region as fixed factors. This model will estimate the adjusted Odds Ratio between treatment arms, its corresponding 95% and P-value.

- ESS clinical response, defined as ESS absolute decrease from baseline of at least 3.0 points, after 2 and 6 weeks of treatment.
- ESS clinical response, defined as $ESS \leq 10$ after 2 and 6 weeks of treatment.
- ESS clinical response, defined as either $ESS \leq 10$ after 2 and 6 weeks of treatment or ESS absolute decrease from baseline of at least 3.0 points after 2 and 6 weeks of treatment.

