The effect size of Bavisant in EDS is unknown. Smaller changes in ESS may be detected that may be clinically useful. In addition, although higher variability is expected in this multicentre study, variability may be lower as the selection criteria restricts a baseline ESS > 12.0 points (compared to 10.0 by other studies). Therefore, in order to confirm both the intragroup statistical decrease in daytime sleepiness together with the intergroup statistical comparison vs. placebo, a total sample size of 200 completed subjects (50 per treatment group + expected 15% of early withdrawal rate) is proposed in this planned first study. The study will be powered to detect a minimum 3.0 point difference in the ESS change from baseline compared to placebo assuming an SD range from 4.0 to 5.3 ( $\alpha$ =0.05;  $\beta$ =0.20; power=80%;  $\Delta$ =3.0; SD=5.0).

Finally, a placebo control group has been considered relevant for the study among other reasons because the primary endpoint is a self-reported assessment, subjective by nature. This subjectivity is controlled by intra-subject comparisons compared to baseline score, and by statistical methods (ANCOVA and MMRM models); but an additional control group with placebo could be considered as the natural progression of the EDS within a clinical trial environment. In any case, the subjects will be informed about the possibility of receiving placebo, the possible consequences and their right to withdraw from the study at any time.

Amendment 04, Final Version 1.0
Protocol No.: BB-2001-201b
EudraCT No.: 2017-000877-35
Page 43 / 142

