#### 11.0 Statistical Methods and Determination of Sample Size

#### 11.1. Statistical and analytical plans

The statistical analysis will be performed by the Department of Biostatistics of Linical, using SAS® version 9.2 or later.

Statistical significance will be assessed for two-sided probability values < 0.05.

All descriptive variables will be tabulated. Quantitative variables will be described showing their number of available and missing observations, mean, median, standard deviation (SD), the range (minimum and maximum) and the first and third quartiles. Frequency and percentage will describe qualitative variables. Missing values will be tabulated with their frequency but will not be included in the calculation of percentages.

The main population for the efficacy analysis will be the intent to treat population (ITT). The per protocol population (PP) will be analysed also as a sensitivity analysis.

The main population for the safety analysis will be the safety population (SAF), defined as all the subjects who have received at least one dose of study treatment.

Full details of the statistical analysis will be given in a Statistical Analysis Plan (SAP) which will be prepared, approved and signed before the database closure, and so before the subjects' evaluability assessment.

Any deviation from the original SAP will be included and reported in the clinical study report (CSR).

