#### 11.1.5 Secondary Efficacy Analyses

All secondary variables assessing a mean absolute or a mean relative change will follow a similar methodology as for the primary variable; i.e., mean changes of ESS (up to 2-week treatment period), SCOPA-Sleep (up to 2-week and 6-week treatment period), PDSS-2 (2-week and 6-week), MWT (6-week), polysomnography (6-week), UPDRS Part III (2-week and 6-week), motor function assessed by the wrist worn device (6-week), HAM-D (2-week, 6-week and follow-up), MoCA (6-week), and FSS (6-week).

The percentage of subjects who showed ESS clinical response (defined as an ESS decrease from baseline of at least 3.0 points and/or final ESS score ≤10) after 2 and 6 weeks of treatment will be described and compared between groups by means of a Chi-square test (or Fisher's exact test according to corresponding applicability). Percentages and difference between treatments will be expressed with their 95% confidence interval calculated with a binomial exact method.

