5 SAMPLE SIZE AND POWER ESTIMATION

A total of 200 completed subjects will be evaluated for the study (50 completed subjects per treatment group, with expected early withdrawal rate of around 15%).

The assumptions used for the sample size calculation are a mean absolute change in the Epworth Sleepiness Scale (ESS) from baseline to the end of the 6-week treatment period of at least 3.0 points (minimum change considered as clinically relevant) and a standard deviation of 5.0 (based on a comparable study of Modafinil in a similar population recruited at one centre (3) which showed a standard deviation in the ESS between 3.5 at baseline and 4.8 at the end of the treatment period) and a reduction in ESS of 2.7 points for subjects treated with Modafinil.

The confirmation of the hypothesis of detecting a mean difference in ESS of 3.0 points vs. baseline requires a sample size of 25 subjects per group (intragroup $\Delta=3.0$; $SD=5.0$; two-side $\alpha=0.05$; $\beta=0.20$; power=80%; one-sample t-test).

The additional endpoint of showing a statistically significant difference of at least 3.0 points in ESS between Bavisant and placebo requires a sample size of 50 subjects per group (between treatment $\Delta=3.0$; $SD=5.0$; two-side $\alpha=0.05$; $\beta=0.20$; power=80%; two-sample equal-variance t-test).

The effect size of Bavisant in EDS is unknown and smaller changes in ESS may be clinically useful according to its profile, and higher variability is expected in this multicentre study; so the sample size of 200 completed subjects (50 per treatment group) is proposed in order to cover both the confirmation of an intragroup change of at least 3.0 points vs. baseline, and the between-group difference of at least 3.0 points change vs. placebo.

The Maintenance of Wakefulness Test (MWT) will be performed in a minimum of 20 subjects per group (80 overall) in order to be enough to show statistically significant differences if the expected MWT absolute change from baseline differs at least in one standard deviation (effect size = 1.0).

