9.2 Secondary Endpoints for Efficacy

9.2.1 Epworth Sleepiness Scale (ESS)

- ESS mean absolute change from baseline to the end of the 2-week treatment will be defined as Total ESS score at visit 2 – Baseline ESS score.
- ESS clinical response, defined as:
 - o First approach: ESS absolute decrease from baseline of at least 3.0 points, after 2 and 6 weeks of treatment.
 - o Second approach: $ESS \leq 10$ after 2 and 6 weeks of treatment.
 - o Third approach: Either $ESS \leq 10$ after 2 and 6 weeks of treatment or ESS absolute decrease from baseline of at least 3.0 points after 2 and 6 weeks of treatment.
- Mean relative change in the ESS from baseline to the end of the 2-week and 6-week treatment periods (percentage of absolute decrease compared to baseline ESS). For each patients the relative change will be calculates as:

Relative change: $(\text{post-baseline evaluation} - \text{baseline evaluation}) / \text{baseline evaluation}$

The same missing imputation strategy as used for primary endpoint will be used for the ESS secondary endpoints (see section 9.1 and 10.4.2 for reference).

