10.4.2 Handling of missing data

- For primary analysis, as describes in section 9.1, post-baseline ESS will be imputed through a Multiple Imputation Jumping to Reference Model.

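### SAP 10.2 gives SCOPA-Sleep, PDSS-2, UPDRS III and HAM-D a single-visit week-6 ANCOVA with no rule for a visit still missing after re-allocation; the MMRM already written for ESS would use their week-2 values.

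*SAP*

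**What the plan says.** Protocol 11.1.5: "All secondary variables assessing a mean absolute or a mean relative change will follow a similar methodology as for the primary variable". In protocol 11.1.4 the primary method includes a missing-data rule: a missing week-6 ESS counts as treatment failure, with a reduction of 0.

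SAP 10.2: "All secondary endpoints evaluated through a mean absolute change will follow a similar statistical analysis as for the primary variable". The bracket that follows lists only the ANCOVA terms: the endpoint's own baseline, treatment and region.

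Missing data in the SAP:

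- **Imputation.** Section 10.4.2 has one rule: "post-baseline ESS will be imputed through a Multiple Imputation Jumping to Reference Model". Section 9.2.1 extends it: "The same missing imputation strategy as used for primary endpoint will be used for the ESS secondary endpoints". No other scale has such a sentence.
- **MMRM.** Section 10.1.2 specifies it as a sensitivity analysis of the primary endpoint, with baseline ESS as covariate.
- **Re-allocation.** Section 4.1 lets an early-termination or unscheduled value fill a missing visit 2 (days 10 to 21) or visit 3 (days 22 to 45). Sections 9.2.2, 9.2.3 and 9.2.6 repeat this for SCOPA-Sleep, PDSS-2 and UPDRS III. HAM-D has only the general rule.
- **Missing items.** Most scale sections say when a total score is not calculated. None says what happens when the visit itself is still missing.

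SAP section 14 declares no changes from the protocol's statistical content.

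**The concern.** For ESS the SAP takes two steps: re-allocate, then impute what is still missing. For the other scales it takes the first step and stops. A subject who attends week 2 and then leaves with nothing in days 22 to 45 contributes nothing to the week-6 ANCOVA, although SCOPA-Sleep, PDSS-2, UPDRS III and HAM-D are all measured at both visits.

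Motor control and depression are named in the secondary objectives, and about 15% of subjects are expected to withdraw. If those who leave differ from those who stay, and differ in another way on active than on placebo, the week-6 contrast moves. The gap in the text also leaves the programmer to choose the rule, which SAP section 1 says the plan should prevent.

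**Working it through.** **1. The plan's own figure.** The documents give no SD, effect or power for these four scales. The only sizing is for ESS: "showing a statistically significant difference of at least 3.0 points in ESS between Bavisant and placebo requires a sample size of 50 subjects per group", with SD 5.0 and 80% power; protocol 11.1 sets the test: "Statistical significance will be assessed for two-sided probability values < 0.05". Recomputed, the t-test needs 45 per group. At 50 per group power is 84.4%, and 50 gives 80% only at SD 5.3, the top of the range in protocol 7.2 ("assuming an SD range from 4.0 to 5.3"). The stated size is thus conservative, and this does not bear on the point. It supplies the scale of the problem: 230 randomised / 4 is about 57 per arm, and 15% of 57 is about 9 leavers per arm.

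**2. Who is omitted at week 6.** An early-termination value before day 10 fits no window. One from days 10 to 21 can fill only visit 2. One from days 22 to 45 fills visit 3. The omitted subjects are those who leave too early for the week-6 window, and later leavers with no early-termination assessment. For leavers after day 14, days 22 to 42 are 21 of the remaining 28 treatment days, so many could be recovered if they attend.

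**3. Precision under random dropout.** Let m be the share unobserved at week 6 and r the week-2/week-6 residual correlation. In large samples

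SE ratio (observed-case / MMRM) = sqrt{ [1/(1−m)] / [1 + (1−r²)·m/(1−m)] }.

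- m = 0.15, r = 0.7: sqrt(1.176/1.090) = 1.04
- m = 0.075 (half recovered), r = 0.7: sqrt(1.081/1.041) = 1.02

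Simulation with 57 per arm and none recovered gave 0.178 against 0.170, a ratio of 1.05. Neither method was biased.

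**4. Bias under selective dropout.** Assumptions, none from the documents: true effect 0.50 SD at week 6 and 0.30 SD at week 2; r = 0.7; in the active-selective case 18% leave active with probability rising as the week-2 score worsens, and 10% leave placebo at random; recovered values carry the week-6 effect.

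| Selective dropout on | In-window values recovered | Observed-case ANCOVA |
|---|---|---|
| active only | none | 0.61 |
| active only | half | 0.55 |
| active only | 75% | 0.52 to 0.53 |
| placebo only | none | 0.40 |
| placebo only | half | 0.46 |
| both arms, 15% in each | none | 0.50 |

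The MMRM gave about 0.50 in every scenario.

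The pattern follows from bias = r × m/(1−m) × E, where E is how much worse, in SD at week 2, the unobserved are than their whole arm. For active only, 0.11 = 0.7 × (0.18/0.82) × E gives E = 0.72. Halving m to 0.09 gives 0.7 × (0.09/0.91) × 0.72 = 0.05, hence 0.55.

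**5. A second illustration on the ESS scale.** True effect 3.0 points, SD 5, week-2 effect 2.0, r from 0.5 to 0.7, 15% dropout overall, none recovered. A missing-at-random model using week 2 gave about 3.0 throughout. Observed-case ANCOVA gave 3.34 to 3.51 with selection on active only, 2.50 to 2.64 on placebo only, and 2.85 to 2.89 when one common function of the week-2 score applied to both arms. That function removes more placebo than active subjects (about 18% against 12%), which explains the small understatement; with equal shares removed, step 4 shows none.

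**6. Jump-to-reference for comparison.** With 15% random dropout and none recovered it gives 3.0 × (1 − 0.15) = 2.55. It does not recover 3.0, because it targets a different quantity.

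**The case against.** The strongest reply is that the plan already deals with most of this. Section 4.1 is a missing-visit rule, the protocol asks for all visit-3 procedures at early termination, and recovery shrinks the bias quickly. That stands, and it rules out calling this a completers analysis, as a reader might infer: a subject who stops on day 25 and attends early termination is included at week 6.

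A reader might also infer that the method favours the drug. The documents do not support a direction. They give no arm-specific withdrawal. The adverse-event rates listed in protocol 7.2 are for 10 mg/d, and the same section says they were lower at 1 and 3 mg. Nothing links withdrawal for insomnia or nausea to a poor week-2 score on these scales.

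Nor are week-2 data ignored across all secondary measures. Week 2 is its own endpoint for the four scales, and MWT, polysomnography, MoCA and FSS have no week-2 measurement.

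Finally, the similarity wording in both documents could be read as carrying the primary's imputation. This does not settle the matter. The SAP's bracket names only model terms, and section 9.2.1 would be redundant if imputation carried over automatically. It would also be unclear which rule carried over: the protocol's zero reduction or the SAP's jump-to-reference. So a flat contradiction of the protocol is not shown, but an unstated rule is.

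**Conclusion.** The point holds as a gap in specification with a modest, conditional effect. For SCOPA-Sleep, PDSS-2, UPDRS III and HAM-D the week-6 analysis as written is observed-case after re-allocation, and it sets aside week-2 information from subjects missing at week 6.

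The sure cost is small: an SE 4% to 5% larger at 15% random dropout with none recovered, and less with recovery. Bias arises only if dropout selects on week-2 response differently by arm. It is then about 0.1 SD in either direction on a true 0.50 SD with no recovery, and about half that with half recovered. These sizes rest on assumed dropout patterns, correlations and effects, and on recovered values carrying the full effect.

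These are secondary endpoints without multiplicity adjustment, so this is a cheap improvement and does not threaten the primary result.

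**What to change.** In SAP 10.2 and 10.4.2:

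- Analyse SCOPA-Sleep, PDSS-2, UPDRS III and HAM-D on the ITT set of SAP section 6 with the 10.1.2 MMRM: weeks 2 and 6, the scale's own baseline, region, treatment, visit and treatment-by-visit. It can stand alongside or replace the observed-case ANCOVA; say which is the main analysis.
- State that MWT, polysomnography, MoCA and FSS are observed-case after re-allocation, or name another rule.
- Reconcile this with protocol 11.1.5 and with the statement in SAP section 14.

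Jump-to-reference need not be required for every scale. It pulls missing active subjects toward placebo and so would also dilute any harm on HAM-D, UPDRS III or MoCA.

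Cost: SAP wording, reuse of the ESS program and some extra output, with no change to trial conduct. The MMRM relies on missing at random and cannot recover subjects with no value at either visit.

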#### Secondary variables:

All secondary variables assessing a mean absolute or a mean relative change will follow a similar methodology as for the primary variable; i.e., mean changes of ESS (up to 2-week treatment period), SCOPA-Sleep (up to 2-week and 6-week treatment period), PDSS-2 (2-week and 6-week), MWT (6-week), polysomnography (6-week), UPDRS Part III (2-week and 6-week), motor function assessed by the wearable tool (6-week), HAM-D (2-week and 6-week), MoCA (6-week), and FSS (6-week).

Percentage of subjects who showed ESS clinical response (defined as an ESS decrease from baseline of at least 3.0 points and/or final ESS score  $\leq$ 10) after 2 and 6 weeks of treatment will be described and compared between groups by means of a Chi-square test (or Fisher's exact test according to corresponding applicability). Percentages and difference between treatments will be expressed with their 95% confidence interval calculated with a binomial exact method.

Adverse events (AEs), adverse events of special interest (AESIs), serious adverse events (SAEs), serious and related adverse events will be coded using the latest available MedDRA version and their corresponding incidences will be summarised as overall events, related events, and events by intensity. AEs will be summarised by MedDRA preferred term and system organ class (primary SOC). Summaries of AEs by preferred term and decreasing frequency and by maximum severity will also be prepared.

Physical examination changes, vital signs changes, laboratory tests changes, cardiovascular changes, ocular changes, suicidal ideation (C-SSRS) findings, and positive psychotic symptoms (BPRS+) findings will be

Amendment 04, Final Version 1.0
Protocol No.: BB-2001-201b
EudraCT No.: 2017-000877-35
Amendment 04, Final Version 1.0
07/Nov/2018
Page 24 / 142

described for the different treatment groups and assessed as either clinically or non-clinically significant findings.

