## 8.4.1.15.9 Free Living Activity

Approximately half (50%) of subjects participating in the clinical study will be offered an opportunity to take part in the assessment of free living activity as an exploratoty assessment. A wrist-worn actigraphy device (GENEActiv®) will be provided to these subjects and they will be required to wear the actigraphy device on their non-dominant wrist for 7 consecutive days during the baseline period (day -7 to day -1) and 7 consecutive days **before** the last dose on visit 3 (day 35 to day 42).

The wrist-worn actigraphy device (GENEActiv®) is a tri-axial accelerometer which provides an objective measure of physical activity levels. A study manual with instructions will be provided to both the investigators and the subjects.

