9.3 Exploratory Efficacy Endpoints

- Free living activity assessed by means of wrist-worn actigraphy.

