10.3 Exploratory Efficacy Analysis

We aim to characterise the changes in free-living activity by means of wrist-worn actigraphy. GENEActiv accelerometers are worn on the wrist and measure tri-axial acceleration with a sample

frequency of 100Hz. The device also measures temperature and light levels. The data is collected pre- and post- dosing (V3), each over a period of seven days. We aim to measure differential physical activity behaviour, and also the length and frequency of daytime sleep episodes.

The data is to be processed using the calibrated GENEActiv tracker data pre-processing package in R. We extract 12-hour daytime records and convert the accelerometer to gravity-subtracted Signal Vector Magnitudes (SVMgs), which is our measure of instantaneous physical intensity. The time-series is downsampled (100x) to one second intervals by averaging the instantaneous SVMgs across the 100 time points. The averaged SVMgs are grouped into four intensity levels groups: Sedentary (< 4.5), Light (4.5-16.5), Moderate (16.5-42), and Vigorous (> 42). These threshold boundaries may change as thresholds used in existing studies are calibrated for different populations. The summary statistics we aim to extract are bout lengths and frequencies, where a bout is a continuous episode of physical activity at a specific intensity levels band. Using paired t-tests, we aim to demonstrate a reduction in sedentary activity and an increase in light to vigorous activity in the dosed population. Using automatic changepoint detection methods (such binary segmentation methods and its extensions, with the fused lasso total variation regulariser, together with Bayesian approaches such as Dirichlet process hidden Markov models.) for detection of sleep boundary times, we also, independently of activity level measurements, aim to quantify the frequency and lengths of daytime sleep episodes.

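### Wrist-device 'motor function' is analysed as a secondary endpoint that is defined nowhere; the device's planned outputs are exploratory activity measures that could move with time awake alone

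*SAP*

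**What the plan says.** Three places treat the item as secondary. The protocol Summary, under secondary variables, has "motor function assessed by the wearable tool (6-week"). Protocol 11.1.5 has "motor function assessed by the wrist worn device (6-week"). SAP 10.2 repeats the item, "Motor function assessed by the wrist worn device (6-week"), and gives the method: "ANCOVA, considering baseline corresponding endpoint evaluation as covariate and treatment and region as fixed factors".

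The device is described differently elsewhere. Protocol 8.4.1.15.9 says that it "is a tri-axial accelerometer which provides an objective measure of physical activity levels", calls the assessment exploratory, and says that about half of the subjects "will be offered an opportunity to take part in the assessment of free living activity". Protocol 6.1.3, 6.2.3 and 8.4.6 also class it as exploratory, as does SAP 3.3. SAP 9.3 lists, as its only exploratory endpoint, "Free living activity assessed by means of wrist-worn actigraphy".

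SAP 10.3 describes the processing. Daytime records of 12 hours are converted to movement intensity and sorted into four bands from sedentary to vigorous. It then states "The summary statistics we aim to extract are bout lengths and frequencies". Daytime sleep episodes are to be detected from the same recordings, separately from the activity measures.

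**The concern.** Motor control is named in the secondary objective. A p-value labelled motor function, printed in the same list as UPDRS Part III, invites the reader to treat it as support for a motor benefit. Two things undermine that reading.

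First, neither document says what the variable is, so the programmer has to choose one. Second, the activity summaries cover a fixed 12-hour day whether or not the subject is awake. Protocol 5.2 gives the promotion of wakefulness as the reason for expecting an effect. A subject who dozes less has more waking time in which to be active, even with unchanged motor signs. The result may then repeat the sleepiness finding under another name. With significance at two-sided 0.05 (Protocol 11.1) and no multiplicity adjustment (Protocol 11.6), nothing in the testing plan guards against that reading.

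**Working it through.** **Step 1. Status of the item, section by section.**

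| Place | Treatment of the wrist device |
|---|---|
| Protocol Summary (secondary variables), 11.1.5; SAP 10.2 | Motor function, secondary, analysed like the primary variable |
| Protocol 6.2.2, 8.4.5; SAP 9.2.1 to 9.2.10 | No wearable endpoint of any kind |
| Protocol 6.1.3, 6.2.3, 8.4.1.15.9, 8.4.6; SAP 3.3, 9.3 | Free living activity, exploratory |

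SAP 14 reports no change from the protocol's statistical content, so it does not settle the conflict.

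**Step 2. Can the variable be derived?** SAP 10.3 gives bout lengths and frequencies by intensity band, and the frequency and length of daytime sleep episodes. None is named or scored as motor function. The band thresholds are also left open to change. The line in SAP 10.2 cannot be programmed from the text.

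**Step 3. Which analysis applies to the device data?** Four descriptions exist:
- descriptive statistics by arm (Protocol 6.2.3 and 8.4.6);
- the primary variable's methodology, as exploratory (Protocol 11.1.6);
- ANCOVA, as secondary (Protocol 11.1.5 and SAP 10.2);
- paired t-tests in the dosed population (SAP 10.3).

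The last is a before-after test with no placebo comparison, although the exploratory objective is a comparison with placebo. In the SAP, the 10.2 line is the only analysis of the device that compares arms.

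**Step 4. Could time awake alone produce a difference?** The documents give no figure for daytime sleep, for the active share of waking time, or for the SD of active minutes. The plan has no figure of its own to reproduce here. What follows is an illustration on assumptions.

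- Record length (SAP 10.3): 12 h = 720 min.
- Assumed baseline daytime sleep: 60 to 180 min. Assumed reduction: 15 to 60 min.
- Assumed active share of waking time: 30% to 50%, identical before and after, so behaviour while awake does not change.
- Change in active minutes = active share × reduction in sleep.

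Smallest case: 0.30 × 15 = 4.5 min. With 60 min baseline sleep, baseline active time is 0.30 × (720 − 60) = 198 min, so the rise is 4.5/198 = 2.3%.

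Largest case: 0.50 × 60 = 30 min. With 180 min baseline sleep, baseline active time is 0.50 × (720 − 180) = 270 min, so the rise is 30/270 = 11.1%.

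Sedentary-class time falls by the same number of minutes. Active time per waking minute stays at 30% or 50%, so the artefact vanishes on that scale.

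Taking half of 50 completers gives 25 device subjects per arm. With an assumed SD of 20 to 40 min and a two-sided two-sample t-test at 0.05, the chance of a nominally significant difference from this mechanism alone is:

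| Shift in active minutes | Chance (SD 40 to SD 20) |
|---|---|
| 4.5 | 7% to 12% |
| 15 | 26% to 74% |
| 30 | 74% to 99.9% |

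The range runs from near the nominal 5% to near certainty. It shows that the mechanism can matter, not how large it is here.

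**The case against.** Several stronger readings are tempting, and the documents do not support them.

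- **That the device measures only the amount of activity.** SAP 10.3 also takes intensity bands, bout structure and daytime sleep episodes from it. Reduced dozing would be visible beside the activity result.
- **That a wake-promoting drug would show a motor benefit.** It could. The variable is undefined, and the situations on the ESS form in Appendix 18.3 are mostly stationary ones such as reading or watching television. A subject who stays awake in them may remain in the sedentary band, and then the shift is zero.
- **That an extra waking hour moves 1/12 = 8.3% of the record.** That is a ceiling. It assumes a full extra hour awake, all of it spent above sedentary.
- **That the motor objective depends on the wearable.** Protocol 6.2.2 and 8.4.5 already label UPDRS Part III as motor control.
- **That use in about half of the subjects disqualifies it as secondary.** MWT and polysomnography are also subset endpoints.

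It is also fair to say that the secondary label carries little formal weight, because all secondary p-values are nominal and the primary analysis is untouched. Simply deleting the SAP 10.2 line would do some harm, since it would leave only before-after tests in the SAP.

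These arguments limit the claim to what could happen, and they shape the remedy. They do not remove the conflict between sections, the missing definition, or the absence of any adjustment for time awake.

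**Conclusion.** The conflict is established from the text alone. Three analysis lists test a wearable motor-function variable as secondary, no endpoint section defines it, and the device is otherwise exploratory free living activity. That part rests on no assumption.

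That a difference could reflect less daytime sleep follows from the fixed 12-hour record and the lack of adjustment for time awake. Its direction would favour the drug if any of the extra waking time is active. Its size is not derivable from the documents, and the figures above hold only under the stated assumptions. UPDRS Part III limits the damage, because the motor objective has its own clinician-rated endpoint. What changes is what may be concluded: an activity result should not be reported as evidence on motor function.

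**What to change.** 1. Delete the wearable motor-function item from the secondary lists in the protocol Summary, Protocol 11.1.5 and SAP 10.2. Report the device outputs as exploratory free living activity.
2. State that UPDRS Part III is the endpoint for the motor-control objective.
3. In SAP 10.3, replace the paired t-tests in the dosed population with a comparison of each dose with placebo, using ANCOVA with baseline, region and treatment as Protocol 11.1.6 implies. Keep the descriptive statistics of Protocol 6.2.3 alongside.
4. Name the activity variables to be analysed and fix the intensity thresholds before database lock. Report activity beside, or per minute of, time awake, using the sleep-episode detection already planned.

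Steps 1 and 3 belong together, because step 1 alone removes the SAP's only between-arm analysis of the device. The cost is one fewer nominal secondary endpoint and a little extra programming. No data collection changes.
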